7.2.2.1. Overall Summary of Adverse Events

All TEAEs will be presented using summary statistics (n and n, %), showing the number of events as well as the number and percentage of subjects with the event.

Table 4: Subcategories For Treatment-Emergent Adverse Events (TEAEs)

Relationship
Related AEs
Not Related AEs
Severity
Mild
Moderate
Severe

The relationship between an AE and the study drug will be assessed as: not related; unlikely related; possibly related; or related. Subjects with at least one related AE and subjects with at least one not related AE will be summarized. Related AEs will include those AEs considered 'possibly related' or 'related' by the investigator; and not related AEs will include those AEs considered 'not related' or 'unlikely related'. The severity or intensity of the severity will be assessed and summarized as mild, moderate, or severe.

The number and percentage of subjects with an event meeting these criteria will be summarized according to the most severe occurrence of an AE for summaries of severity or intensity, and the most extreme relationship of the AE for summaries of relationship to study drug. The number of events will be summarized as reported, with no accounting for the most extreme severity or relationship. Additionally, the number and percentage of subjects who withdrew from the study due to an AE or who died on study will be presented along with the number of events meeting each of these criteria. These statistics will be prepared for all TEAEs and, separately, for SAEs and IARs.

7.2.2.2. AEs, SAEs and IARs by System Organ Class (SOC) and Preferred Term (PT)

The frequencies of TEAEs, SAEs, IARs and percentage of subjects with events will be tabulated by PT within SOC. Subjects are counted once in each SOC and PT. Percentages will be based on the total number of subjects in the specific analysis population. SOCs will be listed in order of frequency of occurrence.

Frequencies will also be presented by the classifications of severity and causality (i.e., relationship to study drug). The incidence of AEs leading to study discontinuation and SAEs leading to discontinuation will also be summarized.

A listing of IARs will be presented for those subjects who had a change in dose. This listing will include the subject number, and the prior dose administered, in addition to the standard adverse event listing elements.

Detailed listings of AEs, SAEs and IARs will be presented. These listings will include severity and relationship to treatment, seriousness, as well as action taken regarding study treatment, other action taken, and subject outcome. A separate listing of subjects who discontinued from the study due to a treatment-emergent AE will also be provided.

7.2.2.3. **Deaths**

A listing of subject deaths and cause of death will be produced, if applicable.

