7.1.3. Medical Events of Interest: Infusion-Associated Reactions

Infusion-associated reactions will be considered AEs of special interest. Any AE that occurs during the infusion or within 4 hours after the infusion is completed and is assessed by the Investigator as at least possibly related to study drug will be designated as an IAR. In addition, if at any time during the study, the Investigator observes symptoms that he/she considers to be consistent with an IAR or hypersensitivity reaction related to the administration of study drug, the symptoms should be recorded as an AE(s) and designated as an IAR(s). Individual AE terms should be recorded rather than 'IAR' or 'infusion-associated reaction'.

As with any ERT, medications and equipment for the treatment of hypersensitivity reactions must be available for immediate use in case of unexpected severe hypersensitivity reactions. These supplies include, but are not limited to, oxygen, antipyretics, antihistamines (e.g., diphenhydramine, parenteral and oral), corticosteroids, epinephrine, beta-adrenergic inhaler, and cardiopulmonary resuscitation devices.

For similar biological products, most acute IARs occur within 2 hours of the infusion. Signs of a possible acute IAR may include: hyperemia, flushing, fever and/or chills, nausea, pruritus, urticaria, gastro-intestinal symptoms (vomiting, diarrhea, abdominal cramping), cardiopulmonary reactions, including chest pain, dyspnea, wheezing, stridor, hypotension, or hypertension.

[Table 6](#) includes dose modifications required for all IARs and general guidance for the diagnosis and management of IARs in accordance with the institution's standard of care. The Investigator should use clinical judgement in the management of IARs in individual subjects participating in this study. In the case of a severe life-threatening reaction, current medical standards for emergency treatment are to be followed.

Table 6 Management of Infusion-Associated Reactions

| Mild Reaction | |
|--|--|

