7.3. Recording of Adverse Events

At each scheduled contact with the subject (or the subject's parent or legal guardian) the Investigator must seek information on AEs by specific questioning and, as appropriate, by examination. Information on all AEs must be recorded in the source document, and in the eCRF. All clearly related signs, symptoms, and abnormal diagnostic procedures results should be recorded under one diagnosis.

AEs will be recorded from the time of signing of the informed consent until completion of the last scheduled visit, i.e., the follow-up visit. Adverse events occurring after signing the informed consent but prior to the first dose of study medication will only be recorded if assessed as related to protocol procedures or requirements.

Any AEs remaining unresolved after completion of the last scheduled visit should be recorded as ongoing. Ongoing AEs/SAEs should continue to be followed up for the period specified in [Section 7.2.2](#) but without further recording in the eCRF. However, follow-up information on SAEs must be reported to the Sponsor or designee as described in Section 7.4. Any SAE that occurs after the study period and is considered to be related to the study treatment or study participation should be recorded and reported immediately.

Any AE that occurs within 24 hours of the infusion will be recorded by time and date. Adverse events occurring 24 hours after the infusion will be recorded by date only. The date and time, or the date when the AE started and stopped, as well as the intensity, seriousness, action taken with regard to the study treatment, causality assessment and outcome of the event will be recorded for each AE.

7.4. Reporting of Serious Adverse Events, Infusion-Associated Reactions and Unanticipated Problems

Investigators and the Sponsor must conform to the AE reporting timelines, formats and requirements of the various entities to which they are responsible (§13 GCP-V; Detailed guidance on the collection, verification and presentation of adverse event/reaction reports arising from clinical trials on medicinal products for human use ['CT-3']; US Code of Federal Regulations Title 21, §312.32, Investigational New Drug [IND] safety reporting).

The Sponsor or designee will report all reportable events to all regulatory authorities, IECs or IRBs, and Investigators as required by local regulations.

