7.2.1. SBC-102 Exposure

Number of weeks in the study and number of study drug infusions received will be summarized overall and; any changes in dose will be described in listings, and may also be provided in tabular summaries.

Exposure to study drug (SBC-102) will be summarized overall doses for the following parameters: the total number of infusions attempted, the number of infusions completed both without and with a rate change or infusion interruption and the number of infusions where the entire infusion volume was not administered will be presented. In addition, a summary will be provided showing the number of weeks on specific doses.

A data listing will be presented, sorted by subject within initial dose of SBC-102, providing the dates, total planned and actual volumes of drug infused, infusion rate and duration of the each infusion along with any modification to the infusion.

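### The planned IAR event count measures recorded symptom terms rather than reactions, and no planned table relates IARs to the number of infusions given

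*SAP*

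**What the plan says.** **Recording.** Protocol 7.1.3 treats IARs as events of special interest and instructs that "Individual AE terms should be recorded rather than" one entry naming the reaction; each such term is designated an IAR. Protocol 7.3, the general recording section, instructs: "All clearly related signs, symptoms, and abnormal diagnostic procedures results should be recorded under one diagnosis". Neither section refers to the other.

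**Counting.** SAP 7.2.2.1 summarises treatment-emergent events "showing the number of events as well as the number and percentage of subjects with the event". Subjects are classified by their worst severity and strongest relationship. For events, the rule is "The number of events will be summarized as reported, with no accounting for the most extreme severity or relationship". The same section adds: "These statistics will be prepared for all TEAEs and, separately, for SAEs and IARs". SAP 7.2.2.2 tabulates IARs by preferred term within system organ class, each subject once per class and term. Neither document defines an IAR episode or merges terms from the same infusion.

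**Exposure.** SAP 7.2.1 summarises "the total number of infusions attempted, the number of infusions completed both without and with a rate change or infusion interruption", along with infusions not given in full and weeks on each dose. These are exposure tables only.

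**Time and dose.** Protocol 8.7.1 planned adverse-event, SAE and IAR frequencies by 24-week interval, plus further displays of IARs over time where appropriate. SAP 4.1 drops the interval table. Protocol 8.7 planned safety by dose as numbers permit; SAP 7.2 names ADA status and unspecified other subgroups, and SAP 7.12 presents adverse events by age. What remains by dose is a listing of IARs in subjects whose dose changed.

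**The concern.** A reader of the safety tables will want to know how many reactions occurred, how severe they were and how often an infusion provoked one. The planned displays answer none of these directly.

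- The event count rises with the number of symptoms entered per reaction. Its severity breakdown has the same problem: a reaction entered as one severe and three mild terms adds one severe and three mild IARs.
- The two recording instructions leave room for the same reaction to be entered as one term or as several.
- The subject percentage counts a subject once regardless of terms, but a subject infused more often has more opportunities to react. Both duration and regimen vary between subjects by design.

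At stake is the interpretability of a named primary safety measure in a single-arm study whose main purpose is safety.

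**Working it through.** The documents give no IAR rate and no infusion count, so there is no stated figure to reproduce. The check has three parts.

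**1. Does the event count follow terms?** Protocol 7.1.3 makes the unit of record the individual term. SAP 7.2.2.1 counts events as reported and applies this separately to IARs. No rule in either document collapses terms. The unit counted is therefore the term. With *k* terms per reaction, 10 reactions give 10*k* events: 10, 20, 30 or 40 for *k* = 1 to 4 (*k* is an assumption).

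**2. How many infusions can a subject receive?** Inputs: at least 52 weeks of treatment (Protocol 3.1); up to 144 weeks, 96 + 48 (Synopsis); at least 8 + 8 every-other-week infusions before weekly dosing (6.1.1); at least 4 + 4 under accelerated escalation, and weekly dosing sooner in special cases (6.1.2).

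Every other week from Week 0 to Week T gives T/2 + 1. After escalation, the count is the every-other-week infusions plus (T − S + 1), where S is the first weekly infusion, taken as two weeks after the last every-other-week one.

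| Path | To Week 96 | To Week 144 |
|---|---|---|
| Every other week throughout | 96/2 + 1 = 49 | 144/2 + 1 = 73 |
| Standard 8 + 8, weekly from Week 32 | 16 + 65 = 81 | 16 + 113 = 129 |
| Accelerated 4 + 4, weekly from Week 16 | 8 + 81 = 89 | 8 + 129 = 137 |
| Special case, weekly from Week 8 | 4 + 89 = 93 | 4 + 137 = 141 |
| Special case, weekly from Week 2 | 1 + 95 = 96 | 1 + 143 = 144 |

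The planned minimum is 52/2 + 1 = 27. Starting weekly dosing one week earlier adds 1 to each escalated figure; giving no infusion in Weeks 97 to 99 lowers 129 to 126.

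Separating duration from regimen:
- Duration alone, every other week: 73/27 = 2.7.
- Regimen at equal follow-up: 81/49 = 1.7 to 96/49 = 2.0 at Week 96; 129/73 = 1.8 to 144/73 = 2.0 at Week 144.
- Both together: 129/27 = 4.8 to 144/27 = 5.3.

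**3. What does this do to the subject percentage?** As an illustration, assume a constant, independent risk *p* per infusion. The documents give no value for *p*. The chance of at least one IAR is 1 − (1 − p)^n.

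| p | n = 27 | n = 73 | n = 129 |
|---|---|---|---|
| 0.5% | 13% | 31% | 48% |
| 1% | 24% | 52% | 73% |
| 2% | 42% | 77% | 93% |

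The same risk per infusion gives very different subject percentages. Between the last two columns only the regimen differs; between the first two, only the duration.

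**The case against.** The case for leaving the plan alone has real substance.

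- **The subject-level measure is sound as regards terms.** The number and percentage of subjects with an IAR, at worst severity, is planned and cannot be inflated by multiple terms. This stands; the term-count problem is confined to the event count and its breakdowns.
- **The SAP sentence concerns severity and relationship.** It contrasts event counts with worst-case subject counts and is not by itself a rule about symptoms. This also stands: multiple counting follows only when it is read with Protocol 7.1.3.
- **Divergent recording is not shown.** A reader might infer that one reaction is one IAR at one site and several at another. The documents do not establish this; a site could reasonably treat 7.1.3 as the specific rule overriding 7.3. They permit divergence, no more. If every site followed 7.1.3, the count would still be of terms.
- **Table 6 of the protocol does not show that a reaction yields five events.** It lists possible signs for grading and management, not signs that occur together.
- **The data are listed and the study is small.** Protocol 8.2 expects about 30 subjects, SAP 9.3 no more than 20. All IARs and all infusions are listed, there is no comparator and testing is not inferential. A reader could rebuild reactions by hand or divide one table by another. But a crude ratio would carry the term-level numerator, and reconstruction from listings is not a prespecified summary.

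**Conclusion.** The point holds in a limited form. The planned IAR event count reflects recorded terms and possibly recording habit, not reactions. The subject percentage is free of that fault but depends on infusions received, and no planned table relates the two. Planned infusions per subject run from 27 to 73 on every-other-week dosing, to 129 with standard escalation and to about 137 to 144 with accelerated or special-case escalation.

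A reader might take the roughly five-fold range as the effect of weekly dosing. It is not: it combines regimen with follow-up, and at equal follow-up weekly dosing accounts for about 1.7- to 2.0-fold.

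These counts are scheduled maxima for each path. They assume escalation at the earliest time, no missed infusions or dose reductions, and, for the Week 144 figures, the full expanded period, which subjects leave once the drug is registered and available in their region. Early discontinuation gives fewer than 27, and the Full Analysis Set requires only one infusion. The documents do not show that any subject follows the longest path.

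Because the analysis is descriptive and the subject counts are valid as counts of subjects, this is a low-cost improvement to a primary safety measure, not a fault that undermines the study.

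**What to change.** In SAP 7.2.2:

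1. Define an IAR episode as all IAR terms linked to the same infusion, with severity equal to that of the worst term.
2. State the linking rule. Protocol 7.3 provides that "Any AE that occurs within 24 hours of the infusion will be recorded by time and date", and SAP 7.2.1 lists the date and duration of each infusion, so most terms can be placed directly. Link an IAR that has only a date to the most recent preceding infusion.
3. Beside the existing subject counts, report the number of episodes, the number and percentage of infusions with at least one IAR, and episodes per 100 infusions, overall and by regimen as numbers permit.
4. Keep the term-level table, labelled as a description of symptoms.

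Separately, reconcile the recording instructions in Protocol 7.1.3 and 7.3. That would need a protocol amendment, but the SAP change does not depend on it: grouping by infusion gives one episode whether a reaction was entered as one term or several.

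The cost is one derived variable, one extra table and a linking rule that may misassign a few delayed IARs. No new data collection is needed.

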7.2.3. Laboratory Tests

Observed measurements and changes from Baseline to each study time point in clinical laboratory data will be summarized. Frequencies of results relative to the laboratory normal range as well as shift tables showing the change from baseline to post-baseline relative to the normal range will be summarized, if sufficient data are available for analysis. Summaries will be presented for liver function tests, serum lipids, hematology, serum chemistry, HbA1c, and coagulation parameters as identified in Table 2, Clinical Laboratory Tests, above.

Plots of mean observed values, absolute change from baseline and mean percent change from baseline over time with standard error bars may be prepared for the following:

- Liver function tests: ALT/AST, GGT, total bilirubin, direct bilirubin, indirect bilirubin, albumin, alkaline phosphatase
- Lipids: total cholesterol, LDL-C, non-HDL-C, HDL-C, triglycerides
- Hematology: hemoglobin, platelets

Also see Section 7.3.2 Clinical Laboratory Tests as described in the Efficacy Analyses section.

7.2.4. Child-Pugh Status

Using the Total Child-Pugh score, subjects will be classified into categories A (score 5 to 6), B (score 7 to 9), and C (score 10 to 15). Higher scores and higher categories represent a worse outcome.

Total Child-Pugh scores will be summarized as a continuous endpoint showing the observed values at baseline and each post-baseline visit, as well as the change from baseline and the percent change from baseline to each post-baseline visit. This summary will be presented for those subjects with a Class B or C at baseline as well as for all subjects in the FAS.

The number and percentage of subjects in each of the categories (A, B, and C) will be summarized for each visit at which the test was performed. In addition a shift from baseline will be presented showing improvement, no change, and decline. Generally, percentages will be based on the number of subjects with baseline and post-baseline results. However, percentages for shifts of improvement (i.e., B to A, C to B, and C to A) will be based on subjects who had scores of B or C at baseline. Similarly, percentages for shifts of worsening (i.e., A to B, A to C, and B to C) will be based on subjects who had scores of A or B at baseline.

7.2.5. Physical Examination

A summary of findings including liver size, spleen size, lymphadenopathy and arterial disease at Screening and follow-up will be presented for baseline and each post-baseline visit.

Summaries of liver and spleen size will include the percentage of subjects with palpable and non-palpable organ, the regularity (smooth or nodular), and the sensitivity (tender or non-tender).

Summaries of lymphadenopathy will include whether any lymphadenopathy is present (yes/no) and the presence/absence and tender/non-tender status of each of five specific regions: cephalic, cervical, clavicular, axillary and inguinal.

Summaries of arterial disease will include the number and percentages of subjects with a pulse result (not palpable, faint, diminished, normal, bounding) in each of four categories (left posterior tibialis, right posterior tibialis, left dorsalis pedis, and right dorsalis pedis. Results will be presented for baseline and each post-baseline visit.

7.2.6. Vital Signs

Observed values, change from baseline, and percent change from baseline will be presented for the following vital sign parameters:

- Body temperature.
- Pulse rate.
- Blood pressure.
- Respiratory rate.

Baseline values will be the average of at most three measurements taken prior to the first infusion, and post-dose values at each visit will be the average the measurements taken as part of that visit including pre-infusion, during infusion, and post-infusion measurements. A listing of the vital signs measurements will be also provided.

7.2.7. Electrocardiograms (ECG)

Categorical summaries (e.g. normal, abnormal, abnormal clinically significant) and a shift from baseline to post-baseline visit will be presented. The shift from baseline will be categorized as no change and worsening. The number of subjects with a worsening ECG will include shifts from Normal to Abnormal – NCS, Normal to Abnormal – CS, and Abnormal – NCS to Abnormal – CS. The percentage of subjects worsening will be based on the number of subjects with ECGs at baseline of Normal or Abnormal-NCS and a post-baseline result. All other percentages in the shift table will be based on the number of subjects with both a baseline and a post-baseline evaluation. A listing of ECG results will be provided.

7.2.8. Denver II Developmental Screening Test (DDST)

The instrument screens children's performance in four developmental domains: personal-social, fine motor-adaptive, language, and gross motor with respect to the age-matched population. The overall results from DDST are expressed as Normal, Abnormal, Questionable, and Untestable.

DDST results will be listed. The results will also be summarized with the number of subjects who had the test done and tested 'normal', 'suspect', or 'untestable' by visit. A shift of the change from baseline to post-baseline result will also be summarized; percentages in the shift table will be based on the number of subjects in the FAS with baseline and post-baseline results.

7.2.9. Antidrug Antibody (ADA) Titer

A subject will be considered as having been ADA positive if the test was reactive and specific.

ADA data will be reported in the subject listings. The number and percentage of subjects who became ADA positive, and the number and percentage of subjects who were positive to neutralizing antibodies will be presented. Should at least 5 subjects be ADA-positive, then additional analyses will be performed to include: time to peak titer; ADA titer by time point; and median and peak ADA titer. Time to peak ADA titer will be analyzed by Kaplan-Meier method; if no titer is detected, time to peak titer will be censored at the date of the last visit during treatment with SBC-102.

Other exploratory analyses of the effect of ADAs on the safety of SBC-102 may also be performed as suggested by the type and amount of data available.

7.3. Efficacy Analyses

Efficacy will be examined for the FAS and, as subject numbers permit, stratified by ADA status, and for other subgroups of interest. Summaries will be provided in the event that at least 5 subjects are included in each subgroup defined by a characteristic (eg. at least 5 subjects with ADA positive and ADA negative).

Efficacy of SBC-102 is expected to be reflected through changes in liver and spleen fat content and organ volume, clinical laboratory data and, where applicable, growth parameters. Evaluation of change in parameters will be made from key assessment time points to the pre-dosing baseline and, as appropriate, to dose-specific baseline assessments (i.e., the assessments taken just prior to escalation to a higher dose level). Additional comparisons of change between sequential assessment time points may also be made.

For continuous endpoints, the observed values, change from baseline and percent change from baseline at each time of assessment will be summarized, and will include 95% confidence intervals.

